5.1 Screening Period Criteria

Inclusion:

- a. Male or female patients who are at least 18 years old and younger than 75 years of age at the time of screening visit
- b. Patients with End-Stage Renal Failure (ESRD) who are chronically receiving hemodialysis and have anemia
- c. Patients with a mean baseline Hb concentration within Hb level ≥ 9 g/dL during the screening period
- d. Haemodialysis patients with anemia associated with Chronic Kidney Disease (CKD) currently receiving stable maintenance therapy with Epoetin at least once per week
- e. Adequate iron substitution status (serum ferritin ≥ 100 $\mu\text{g} / \text{L}$ (100 ng / mL) or saturated transferrin levels $\geq 20\%$)
- f. Patients who understand the information provided to them or their representatives and may provide written consent.

Exclusion:

- a. Contraindication with Epoetin therapy
- b. Documented active bleeding in the last 12 weeks prior to screening period
- c. Any blood transfusion within the last 2 weeks prior Screening period
- d. History of malignancy of any organ system within the last 5 years
- e. Patients with uncontrolled hypertension (in case the mean value of diastolic blood pressure as measured 4 times during the baseline observation period is 110 mmHg or more).
- f. Patients hyporesponsive epoetin treatment or had medical history of experiencing pure red blood cell forming failure after being administered with Epoetin products
- g. Known bone marrow fibrosis (osteitis fibrosa cystica)
- h. Patient with serious cardiovascular disorders: myocardial infarction, patients with congestive heart failure (NYHA class III or higher), ischemic vascular disease
- i. Patient received percutaneous coronary intervention (PCI), or coronary artery bypass grafting (CABG) during the last 6 months prior to screening

- j. Patients with ALT or AST exceeding the upper limits of the normal level by more than 5-folds
- k. Patients whose kidney transplant is expected or already planned for survival
- l. Secondary anemia to other causes different to the CKD (aplastic anemia, hemolytic anemia, sickle cell anemia, multiple myeloma, leukemia, myelodysplastic syndrome)
- m. Patients with the following diseases and who are considered unfit to enroll in the clinical study: mental system disease, mental disease, drug intoxication, epilepsy, lung infarction, cerebral infarction, positive HIV antibody, systemic lupus erythematosus, immunosuppressive condition and general infection
- n. Pregnancy or lactation period in female patients, or women of childbearing potential without an effective method of birth control
- o. Patients who were considered unfit for study by the principal investigators or by the co-investigator

5.2 Baseline Evaluation Period Criteria

Subject who voluntarily consented to participate in the clinical study, meet eligible criteria, stable with Eprex®, will be evaluated again to assess the subject eligibility prior randomization and maintenance period. Only subjects who meet eligible baseline criteria will continue to randomization and maintenance period.

Inclusion criteria

- a. Subject achieved Hb target 10-12 g/dl
- b. Adequate iron substitution status (serum ferritin $\geq 100 \mu\text{g} / \text{L}$ (100 ng / mL) or saturated transferrin levels $\geq 20\%$).
- c. Patients who have gone through the Baseline period at the time of the screening visit or before randomization
- d. Patients with dry weight less than 5% during the baseline evaluation period
- e. Subject are reliable and will willingly cooperate during the maintenance period and observe the restrictions

Exclusion

- a. Any blood transfusion within the last 2 weeks prior to screening period
- b. In case the EPO administration dose during the baseline evaluation period is increased or decreased by 20% or more
- c. Currently contraindicated with Epoetin therapy

- d. Subject administered with prohibited drug (androgen, cyclosporin, and chemotherapy agents)
- e. Occurrence medical condition which can affect efficacy data during maintenance period judged by principal investigator or sub-investigator

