In patients with CKD, a decrease in the glomerular filtration rate causes a buildup of chemicals such as potassium and urea. Hemodialysis therapy, which is a blood cleansing process using a kidney replacement in the form of a dialyzer machine, is given to patients with CK level 5 or the final level or GFR <15 mL / minute / 1.73 m². This process involves the use of a dialysate containing sodium bicarbonate, sodium chloride, acid concentrate, and water distilled as an osmosis medium. The physiological working principle of hemodialysis is filtration, diffusion, osmosis, and ultrafiltration which are influenced by temperature, viscosity, and size of the molecule itself (Vadakedath & Kandi, 2017).

People with CKD often also suffer from anemia complications caused by a decrease in kidney function. Anemia diagnosis is given to adult PGK patients if the Hb concentration is <13 g / dl in men or <12 g / dl in women. This condition can occur when a decrease in kidney function is up to 50%. Iron therapy can be performed on CKD patients with anemia who have low iron levels, which is known by conducting laboratory tests for ferritin <200 ng / L and transferrin saturation <30%. In addition, CKD patients with anemia can be given Epoetin therapy to increase levels of red blood cells or erythrocytes in the blood (Pollock et al. 2008).

Giving Epoetin in patients with CKD who undergo hemodialysis begins after symptoms of uremia, excess fluid, and stable hypertension. In addition, administration of Epoetin can only be done after all causes of anemia except erythropoietin deficiency are overcome, especially iron deficiency, folic acid, vitamin B12, and the presence of bleeding (Pollock et al. 2008).

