2.4 Epodion®

Epodion® is an alpha rhEPO product produced by PT. Daewoong Pharmaceutical Company Indonesia. This product is used in conjunction with other clinical treatments for anemic patients due to chronic kidney disease or due to chemotherapy. Yellowish transparent Epodion® injection solution which can be injected intravenously or subcutaneously. Epodion® has four products with different EPO content, including 2000 IU, 3000 IU, 4000 IU, and 10000 IU.

At the beginning of Epodion® use, patients are given a dose of 50 units/kg of body weight three times a week which can be done intravenously or subcutaneously. If needed, the dose can be increased to 75 units/kg at 4-week intervals from the initial administration. If the increase in hemoglobin level increases by more than 2 gr/dL at the initial dose, the administration of Epodion® must be reduced to 2 times a week. Repair doses can be continued until the patient's hemoglobin level becomes 10 gr/dL. Anemia that has been overcome can be continued with a maintenance

dose of between 25 to 50 units/kg, 2 or 3 times a week. The expected hemoglobin range for treatment is 10-12 gr/dL. The initial hemoglobin level determines the treatment dose. In addition, the patient's age is also important in determining the dose. The dosage for the use of Epodion® should not exceed 200 units/kg and the frequency of administration is not more than 3 times a week. During treatment, the patient's iron levels need to be controlled. Chronic kidney failure patients who do not undergo hemodialysis, a dose of 70-150 units/kg per week is proven to maintain hematocrit levels 36-38% for more than 6 months.

Research on the effects of Epodion® on human bone marrow cell culture shows that Epodion® stimulates the formation of red blood cells and does not affect the formation of white blood cells. Animal studies using Epodion® showed in vivo efficacy in test animals. In addition, no cytotoxic effects were detected, changes in behavior, locomotor activity, circulation or breathing in test animals.

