Often, a higher dose of heparin is needed during hemodialysis due to an increase in hematocrit levels. In addition, a dialysis system blockage may occur if heparinization is not optimal. Shunt thrombosis can occur in patients who tend to be hypotensive or patients with complications of the arteriovenous fistula (eg, aneurysm, stenosis). In these patients it is recommended to give thrombosis prophylaxis to administration of acetalsalate. In some patients, there is a decrease in serum ferritin levels together with an increase in hematocrit. For this reason, it is recommended to provide 200 mg / day of oral iron (Fe²⁺) substitution in patients with serum ferritin levels <100 ug / L or transferrin saturation <20%. Then, there is a temporary increase in serum potassium and phosphate levels. Therefore, it is recommended to monitor these parameters regularly.

CHAPTER 3. STUDY DESIGN OVERVIEW

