6.4 Concomitant Medication and Treatment

6.4.1 Concomitant medication

The following drugs may be concomitantly administered during the study period.

- a. Any drug the subject has been on medication prior to participating in the clinical trial, the drug which is considered not to affect the study result analysis shall be permitted during the study period by the clinician's judgement.
- b. Any drug to be used temporarily for the purpose of treating other diseases or adverse events incurred during the study period shall be concomitantly administered through discussion with the investigator or physician.

All the information (commercial name, indication, daily dose, administration period etc.) of concomitant medications (including medication to treat other diseases or adverse events) shall be recorded in the CRF in detail.

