7.4.1 Primary Endpoint

Change in Hb levels from baseline to the evaluation period

Descriptive statistics will be provided by treatment group. The difference between treatment groups will be determined by ANCOVA (analysis of covariance) model with treatment as factor, and baseline Hb level and the change in weekly dosage per kg body weight from baseline to the evaluation period of Epodion® or Eprex® as covariates.

Therapeutic equivalence of Epodion® to the comparator Eprex® will be demonstrated if the two-sided 90% confidence interval of the difference of mean changes in Hb levels between treatment groups lay within the interval of ± 0.5 g/dL.

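### Baseline iron status is required before randomisation but left out of the primary ANCOVA, and the plan does not say how iron use after randomisation is governed or displayed by arm

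*Protocol*

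**What the plan says.** **Entry.** Protocol 5.1 e and 5.2 b, and the synopsis, all accept a subject whose ferritin is at least 100 µg/L or whose transferrin saturation is at least 20%. The link in 5.2 b reads "100 ng / mL) or saturated transferrin levels". A subject fails only if both markers are low.

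**Background on iron.** Section 1.1 describes standard treatment as exogenous erythropoietin plus correction of iron. Section 2.1 says epoetin should follow correction of other causes of anaemia, iron deficiency in particular. Section 2.4 says "During treatment, the patient's iron levels need to be controlled". It also recommends oral iron for "patients with serum ferritin levels <100 ug / L or transferrin saturation <20"%. Section 2.1 gives different figures: "ferritin <200 ng / L and transferrin saturation <30"%.

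**Conduct.** Section 6.4.1 does not name iron. Item a allows prior drugs judged not to affect the results. Item b allows "Any drug to be used temporarily for the purpose of treating other diseases or adverse events incurred during the study period". Iron is not among the prohibited drugs in 5.2. Chapters 4 to 6 give no procedure for starting or changing iron during maintenance.

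**Analysis.** Protocol 7.4.1 and SAP 3.1 specify an "ANCOVA (analysis of covariance) model with treatment as factor, and baseline Hb level", plus the change in weekly dose per kg, as covariates. Neither document has an iron covariate or a display of iron use.

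**The concern.** The protocol presents iron as a determinant of the response to epoetin, and Hb change alone decides equivalence. Leaving a prognostic measure that is already required before randomisation out of the model gives up precision at no saving.

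The second issue is conduct. Investigators know the treatment, and no study procedure covers iron during maintenance. One investigator could start iron in a subject with one low marker, following section 2.4. Another could leave the same subject alone, since the entry rule calls the iron status adequate. If such decisions differed by arm, part of the Hb difference would come from iron and not from the product, and no planned output would show it.

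**Working it through.** **1. Do the iron passages overlap?**
- Entry (5.1 e, 5.2 b): adequate if at least one marker is at or above its cut-off (100 µg/L, 20%).
- Section 2.4: iron advised if at least one marker is below the same cut-off.
- Both hold exactly when one marker is low and the other is not.
- Section 2.1 requires both markers to be low, at 200 and 30%, with ferritin in ng/L. The entry criteria equate µg/L with ng/mL, so ng/L is a unit 1000 times smaller.

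**2. What share of subjects is this?** The documents give no distribution. Assume 5% to 25% of candidates have low ferritin (a), 10% to 35% have low saturation (b), and the two follow a bivariate normal threshold model with correlation 0 to 0.6. Let c be the probability that both are low.

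Share among those who pass entry = (a + b − 2c)/(1 − c)

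| a | b | correlation | c | share |
|---|---|---|---|---|
| 5% | 10% | 0.6 | 0.024 | 10% |
| 15% | 25% | 0.6 | 0.093 | 24% |
| 15% | 25% | 0 | 0.0375 | 34% |
| 25% | 35% | 0 | 0.0875 | 47% |

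**3. Baseline power.** Inputs from Protocol 3.2: SD 0.8, margin ±0.5, true difference 0, 1:1 allocation, 90 evaluable, one-sided 5% twice (the 90% interval in 7.4.1). With 45 per arm, the standard error is 0.8 × √(2/45) = 0.169. The exact two one-sided t-tests calculation gives 80.5% power. The stated 90% power is not reproduced; it needs 114 evaluable. That is a separate matter, so 80.5% is the reference here.

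**4. Value of an iron covariate.** If baseline iron explains a share R² of residual variance (assumed), the SD becomes 0.8 × √(1 − R²).

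| R² | SD | power at 90 |
|---|---|---|
| 0 | 0.800 | 80.5% |
| 5% | 0.780 | 83.0% |
| 10% | 0.759 | 85.5% |

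Losing two degrees of freedom changes these by less than 0.1 point.

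**5. Differential iron use.** Shift in the Hb difference = gap between arms in the share starting iron × Hb effect of iron.
- Equal use: gap 0, so no expected shift.
- Assumed gap of 10 to 20 points and effect of 0.5 to 1.0 g/dL: from 0.10 × 0.5 = 0.05 to 0.20 × 1.0 = 0.20 g/dL.
- True difference at the margin (0.5), shift toward zero, SD 0.80: the probability of declaring equivalence is 5.0% with no shift, 8.8% at 0.05 and 31.9% at 0.20.
- True difference 0: a shift of 0.05 lowers power to 78.6%, and a shift of 0.15 lowers it to 64.6%.

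**6. Added variance.** If 10% to 30% of subjects (p) start iron and gain 0.5 to 1.0 g/dL (x), SD = √(0.64 + p(1 − p)x²) = 0.81 to 0.92, and power is 78.7% to 63.6%. This holds only if the 0.8 excludes iron-related variance, which the documents do not show.

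**The case against.** A reader might infer that the protocol holds incompatible iron rules. It does not. The study has one iron criterion, stated the same way in the synopsis, 5.1 and 5.2. Sections 2.1 and 2.4 are literature and product background, worded as advice. An entry threshold and supplementation advice serve different purposes, so a subject can meet both without contradiction. Section 6.4.1 is silent on iron and is not a further rule; item b could be read to cover newly found iron deficiency. This objection stands. What remains is an unreconciled overlap and the absence of a study procedure.

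A reader might also infer that many randomised subjects are affected and that iron moves the primary endpoint. Neither is shown. Every iron input above is assumed. The 0.8 comes from an earlier trial and may already include iron-related variance, so step 6 may double count. Dose is adjusted in both arms to hold Hb at 10–12 g/dL, so part of an iron effect would appear as dose. Randomisation balances baseline iron in expectation. The 32% is the worst corner of the assumed range; 9% is the other end.

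Two replies limit this. Randomisation does not balance later iron decisions by investigators who know the arm. And the primary model adjusts for the post-randomisation change in dose, so an iron effect expressed through dose can re-enter the adjusted Hb contrast.

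Omitting an iron covariate is not an error in itself. It is a missed gain in precision.

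**Conclusion.** The point holds as an improvement to the analysis plan, with a supporting clarification of the protocol. A measure that the protocol treats as important, and requires before randomisation, is absent from the primary model. Iron use after randomisation is neither governed nor displayed by arm.

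The gain from adjustment is modest: about 2.5 to 5 points of power at 90 evaluable, if baseline iron explains 5% to 10% of residual variance. The effect of iron use on the Hb difference runs from negligible to material and cannot be fixed from the documents. Bias requires different use by arm, which the open-label design permits but which nothing in the documents establishes. The affected share of 10% to 47% reflects assumed marker distributions only.

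**What to change.** 1. **Primary model.** In Protocol 7.4.1 and SAP 3.1, prespecify as covariate(s) the baseline iron measure(s) recorded for criterion 5.2 b: transferrin saturation, log ferritin, or both, whichever is recorded for all subjects. Because 5.2 b can be met on one marker alone, state how a subject missing the other is handled; SAP 3.4 does not address a missing baseline covariate. Cost: SAP wording and one or two degrees of freedom.

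2. **Supportive display.** Tabulate iron starts and changes after randomisation by arm. Protocol 6.4.1 already requires name, indication, dose and period of each concomitant drug in the CRF, so no new data are needed. Hb values obtained after iron should not be discarded: that would select on a post-randomisation event and create missing data related to Hb.

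3. **Text.** Reconcile Protocol 2.1 (including its ferritin unit), 2.4, 5.1 e, 5.2 b and 6.4.1, so that iron is handled the same way in both arms. Which rule applies is for the sponsor and investigators. Cost: a short protocol clarification.

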5.3 Discontinuation and Dropout Criteria

The subject may discontinue participation in this clinical study at any time by his/her request, or by the investigator or sponsor's discretion for a safety, action or administrative reason. The investigator shall ask the subject dropout reason, ask them to perform the final visit. If applicable, the investigator shall make utmost efforts to follow up the subject's unresolved adverse events.

Patients who dropped out of this study were patients in one of the following cases:

1. Withdrawn of the consent.
2. Subject receives kidney transplantation during the study period.
3. Subjects that are unable to continue the study because of side effects.
4. Subject do not receive investigational product 4 week consecutively.
5. Not able to participate or continue the study or for any reason based on the assessment of the principal investigator.

5.4 Temporary Discontinuation

If the following situation occurs, the investigator shall delay investigational product administration until the situation will be settled. Then, investigational product administration shall be delayed to the extent of investigational product administration schedule indicated.

The following condition when investigational product should be delayed are detailed below:

- Increase blood pressure systole ≥ 180 mmHg and/or diastole ≥ 120 mmHg.
- Hb level exceed 13 g/dL, investigational product should be reinitiated at approximately 25% lower than the previous dose after haemoglobin levels fall to 12 g/dl (7.45 mmol/l) or below.
- Any reason based on the assessment of the principal investigator.

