4.1.2 Secondary Endpoint

1. Obtain data mean change in weekly dosage per kg body weight between the baseline period and the evaluation period.
2. Calculating instability rate of Hb (hemoglobin) level during maintenance and evaluation period as defined when Hb (hemoglobin) level dropped below 8 g/dL or increase more than 13 g/dL.
3. Evaluating Hb (hemoglobin) and hematocrit level during maintenance and evaluation period.

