4.4 Study Procedure

This research consists of a screening period (4 weeks), titration period (4~8 weeks) baseline evaluation period (4 weeks), maintenance period (24 weeks) and 4 weeks for evaluation period. For each subject, the end of the study was the last day of evaluation. In the case of a subject that has left the study (withdrawn), the exit date will be the end of the study.

Procedure and Assessment	Screening	Titration Period				Baseline Period				Maintenance Period																Evaluation Period			
										10/14	12/16	14/18	16/20	18/22	20/24	22/26	24/28	26/30	28/32	30/34	32/36	34/38	36/40						
Week	-4	0	2	4	6	8	10	12																					
Informed consent form	■																												
Patient demography	■																												
Medical history	■																												
Prior Medication	■																												
Inclusion/exclusion criteria	■																												
Baseline Target Evaluation ¹⁾					■	■	■	■																					
Randomization ³⁾						■	■	■																					
Concomitant Medication																													
Eprex® administration ²⁾																													
Epodion® administration ²⁾																													
Lab Test	CBC (Hb)	■	■	■	■	■	■	■	■	■	■	■	■	■	■	■	■	■	■	■	■	■	■	■	■	■	■	■	■
	CBC (Hct)	■																											
	Iron status	■					■																						
	HIV	■																											
	Blood Chemistry (ALT&AST)	■																											
Pregnancy Test	■																												
Safety Assessment ⁴⁾																													

Figure 6. Study method

[figure not shown]

Figure 7. Study flow

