4.4.4 Maintenance Period (Week 9-32/13-36)

During the maintenance period (Week 9-32/13-36), subjects who met the criteria were given Epoetin treatment according to the randomization allocation. Administration of Eprex® or Epodion® will be done with same doses regimen during titration period through intravenous injection. Epoetin dose may be increased or decreased at an appropriate level according to the condition of the subjects. Subject Hb levels were controlled to reach a range of 10-12 g/dL. Blood collection is carried out once every two weeks for the purposes of routine hematological test. Adverse event concomitant medication, and instability rate of Hb data is observed during the maintenance period. Concomitant medication during the study were recorded in the Case Report Form (CRF).

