7.1.2 Full Analysis Set (FAS)

The Full Analysis Set will be consisting of all randomized subjects who treated for at least 4 weeks of the investigational product, and for whom at least 1 Hb level for the evaluation period will be available. In the case of dosing administration error, analyses on the FAS will be conducted according to randomized treatment.

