7.1.3 Per-Protocol Set (PPS)

The Per-Protocol Set will be defined as all subjects who completed the study without any major protocol deviations. The subjects who committed a major protocol deviation will be finally determined in the blind meeting before database lock.

In the study, the efficacy assessment will have the PPS as the primary analysis set, and the FAS will be additionally analyzed and the results of the two analysis sets will be compared.

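### The Hb instability rate leaves out events observed in subjects who exit before the evaluation period, because it requires an evaluation-period Hb

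*Protocol*

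**What the plan says.** **Endpoint.** Protocol 4.1.2 lists as a secondary efficacy endpoint "Calculating instability rate of Hb (hemoglobin) level during maintenance and evaluation period", an event being Hb below 8 or above 13 g/dL. Protocol 7.4.2(2) and SAP 3.2(2) ask for the number and rate of such subjects by arm, and for the between-arm difference, each with a 95% confidence interval.

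**Who is analysed.** Protocol 7.4 and SAP 3 name only the FAS and the PPS for efficacy. The FAS admits randomized subjects treated for at least four weeks and "for whom at least 1 Hb level for the evaluation period will be available" (Protocol 7.1.2, SAP 1.2). The PPS is "all subjects who completed the study without any major protocol deviations" (Protocol 7.1.3, SAP 1.3). Protocol 7.6 and SAP 3.4 repeat the evaluation-period Hb condition for efficacy variables in general, then add that the instability rate is not to be imputed.

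**Hold and exit.** Protocol 5.4 requires product to be withheld when Hb exceeds 13 g/dL, and "investigational product should be reinitiated at approximately 25% lower than the previous dose after haemoglobin levels fall to 12 g/dl" or below. Protocol 5.3 item 4 lists as a dropout case: "Subject do not receive investigational product 4 week consecutively". It says nothing about holds that 5.4 itself requires. At dropout the investigator is to "ask them to perform the final visit". Under 4.4, "In the case of a subject that has left the study (withdrawn), the exit date will be the end of the study".

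**The concern.** The endpoint spans 28 weeks (24 of maintenance, 4 of evaluation), but only subjects who provide an Hb in the last four can contribute. A value below 8 or above 13 recorded at week 16 in a subject who leaves at week 24 is observed data on the endpoint, yet neither the event nor the subject enters the calculation. This applies to any exit before the evaluation period, whatever its cause.

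The hold for high Hb is one such route and deserves attention because the event itself starts it: Hb above 13 triggers the hold, and a hold lasting four weeks ends participation. A subject managed exactly as the protocol directs can therefore leave the analysis because of the event being counted.

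Comparing FAS with PPS will not show the loss, since the subject is in neither set. What is at stake is the accuracy of each arm's rate and, if exits differ by arm, of the between-arm difference.

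**Working it through.** The plan gives no expected instability rate, so there is no figure of its own to reproduce. Event counts below are assumptions.

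**1. Which holds end before the evaluation period?** Inputs: Hb every two weeks (Protocol 4.4.4: "Blood collection is carried out once every two weeks for the purposes of routine hematological test"); on the short track, maintenance readings at weeks 10, 12, ..., 32 (12 readings), evaluation period weeks 33-36, evaluation readings at weeks 34 and 36. I assume the four weeks start on the day of the reading above 13. A hold triggered at week w then reaches its limit at w + 4.

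| Trigger week w | w + 4 | Consequence |
|---|---|---|
| 10 to 26 (9 of 12 readings) | 14 to 30 | Exit clearly before week 33; in neither FAS nor PPS |
| 28 | 32 | Borderline: an Hb at a final visit in week 33 would satisfy the FAS condition |
| 30 | 34 | FAS membership depends on whether the week-34 sample is taken |
| 32 | 36 | Limit reached at the last visit; arguably a completer |
| 34, 36 | 38, 40 | After study end; not affected |

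For the extended track add four weeks throughout.

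**2. How slow must the fall in Hb be?** To restart within four weeks, Hb must fall from its value h to 12, that is by (h - 12)/4 per week:
- h = 13.1: 1.1/4 = 0.275 g/dL per week
- h = 13.5: 1.5/4 = 0.375
- h = 14.0: 2.0/4 = 0.5

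A slower fall leads to exit. The documents give no off-drug rate of fall, so no frequency can be derived.

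**3. Effect when only subjects with an event are lost.** With e true events among n = 50 (the planned arm size) and k lost, the reported rate is (e - k)/(50 - k):

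| e | k = 0 | k = 1 | k = 2 |
|---|---|---|---|
| 2 | 4.0% | 1/49 = 2.0% | 0/48 = 0.0% |
| 5 | 10.0% | 4/49 = 8.2% | 3/48 = 6.3% |
| 10 | 20.0% | 9/49 = 18.4% | 8/48 = 16.7% |

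Exact 95% intervals: 5/50, 3.3 to 21.8%; 4/49, 2.3 to 19.6%; 3/48, 1.3 to 17.2%.

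If both arms truly have 5/50 and only one arm loses events, the difference (Newcombe interval; the plan names no method) is:
- none lost: 0.0 points (-12.7 to 12.7)
- one lost: -1.8 points (-14.2 to 10.6)
- two lost: -3.8 points (-15.8 to 8.3)

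**4. Effect when event-free subjects leave as well.** If m subjects exit early, k of them with an event, the reported rate is (e - k)/(n - m). It falls below e/n only if k/m exceeds e/n. Take the 10% dropout assumed in Protocol 3.2 (Rationale Number of Subject), m = 5 of 50, and suppose all five leave before the evaluation period:
- e = 5, k = 0: 5/45 = 11.1% (true 10.0%)
- e = 5, k = 1: 4/45 = 8.9%
- e = 5, k = 2: 3/45 = 6.7%
- e = 10, k = 1: 9/45 = 20.0% (true 20.0%, unchanged)

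The net error can have either sign, depending on the mix of early leavers.

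**The case against.** **Sections 5.3 and 5.4 are compatible.** A reader might infer that they contradict each other. They do not: 5.4 governs conduct during a hold, and 5.3 item 4 can be read as a four-week maximum, an ordinary choice in a comparison of two products. Exempting holds would put subjects with more than four weeks off product into the PPS, the primary analysis set. This objection stands. The loss comes from the evaluation-period Hb condition; the hold is one route into it.

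**The rate need not be too low.** A reader might infer a downward bias overall. The documents do not support that, because event-free early leavers are removed by the same condition (step 4). The downward direction holds only for losses through the hold route taken alone.

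**The plan already handles this.** Three provisions could be cited, and none restores the subject to the rate. The sentence on observed data rules out imputation; it does not lift the condition stated just before it. The final visit is not defined as an evaluation-period visit and helps only where it falls in week 33 (37) or later. The Safety Set tables of Protocol 7.5 would show an Hb judged clinically significant, and an adverse event leading to discontinuation, by arm. That is useful visibility, but it depends on the investigator's judgement and leaves the rate and its interval unchanged.

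**It will be rare.** Probably so: dosing aims at 10-12 g/dL, Hb is checked every two weeks, and unscheduled re-tests are allowed. This limits the size of the problem but does not remove the mismatch between the endpoint's period and its analysis set.

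**Conclusion.** The point holds as a minor one. The instability rate is defined over maintenance and evaluation but computed only in subjects with an evaluation-period Hb, so events observed in those who exit sooner are lost. That follows from the text of both documents and needs no assumption.

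Its size does rest on assumptions. At 50 per arm and 2 to 10 true events, each event lost alone lowers the arm's rate by 1.6 to 2.0 points. The illustrated one-arm losses shift the difference by 1.8 or 3.8 points, against an interval of about 12.7 points either side. The frequency is unknown and probably low, and the net direction across all early exits is undetermined.

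A reader might also infer that the equivalence conclusion is compromised. Nothing here supports that: the endpoint concerned is secondary, has no success criterion, and does not enter the primary analysis.

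**What to change.** In Protocol 7.4.2(2) and 7.6, and SAP 3.2(2) and 3.4, state that the instability rate is computed on all randomized subjects with at least one post-randomization dose and at least one post-randomization Hb, by randomized arm, using every observed maintenance and evaluation Hb, without the evaluation-period Hb condition. Keep the FAS and PPS versions as sensitivity analyses.

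**Cost.** A wording change, using data already collected. The real drawback is unequal follow-up: a subject who leaves early without an event counts as stable. One who leaves at week 12 on the short track has been observed for 4 of 28 weeks (12 - 8 = 4; 36 - 8 = 28). So also report follow-up time by arm, or give an exposure-adjusted or time-to-first-event rate beside the simple proportion.

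**Optional.** The four-week rule in 5.3 item 4 can stay as a maximum hold. Exempting holds required by 5.4 is a clinical trade-off and is not needed for this fix. Counting by arm the subjects held for Hb above 13, and those who reach four weeks, would show whether the route was used.
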